#### b. Analyses based on comparison of proportions

Assuming alpha=0.0045 (Bonferroni-adjusted for 11 tests), 2-sided test, 1:1 allocation ratio, with a sample size of 2,500 per arm, and 10% attrition, we will have  $\geq 80\%$  power to detect an change in early initiation of breastfeeding of 90.0% vs. 93.1%; bathing and application of substance to cord of 50.0% vs. 55.5%; elevated depression symptom prevalence of 19.0% vs. 14.5%. Assuming 15% of infants are born prematurely or have low birth weight, our analysis of KMC will have a sample size of 375 per arm. Assuming 10% attrition, alpha=0.0045 and 2-sided test, we will have  $\geq 80\%$  power to detect a change in KMC provision of 30.0% vs. 43.7%.

#### c. Analyses based on continuous variables

Assuming alpha=0.0045 (Bonferroni-adjusted for 11 tests), 2-sided test, 1:1 allocation ratio, with a sample size of 2,500 per arm, and 10% attrition, we will have  $\geq 80\%$  power to detect a difference in continuous scores of 0.11: 0.50 vs. 0.61 mean clinic visits, 3.00 vs. 3.11 mean danger signs named, and 2.50 vs. 2.61 mean social support score.

**Table 3.1 Summary of detectable differences**

Indicator	Outcomes (control)	Minimum detectable difference		
		Outcomes (intervention)	Absolute difference	Relative difference
Neonatal mortality per 1000 births 	25.0	13.8	11.2	0.55
	23.0	12.2	10.8	0.53
	20.0	10.0	10.0	0.50
Initiation of BF within 1h; EBF for 6 weeks 	90.0%	93.1%	3.1%	1.03
	80.0%	84.2%	4.2%	1.05
Application of substances to cord; Bath within 24h 	40.0%	45.4%	5.4%	1.14
	50.0%	55.5%	5.5%	1.11
Provision of KMC 	30.0%	43.7%	13.7%	1.46
	25.0%	38.2%	13.2%	1.53
Number of clinic visits in first 6 weeks 	0.50	0.61	0.11	1.22
	1.00	1.11	0.11	1.11
Number of danger signs correctly named 	3.00	3.11	0.11	1.04
	5.00	5.11	0.11	1.02
Maternal depression 	19.0%	14.5%	4.5%	0.76
Maternal social support score; Maternal self-efficacy score (max 4.0) 	2.50	2.61	0.11	1.04
	3.50	3.61	0.11	1.03

 $\alpha$ =0.05, Adjusted  $\alpha$ =0.0045,  $\beta$ =0.8, 2-sided tests

## **4. USE OF INTENTION-TO-TREAT AND PER-PROTOCOL ANALYSES**

Analysis of primary outcomes will be by intention to treat (all participants).

After enrollment had begun, the study team became aware of other SMS health messaging interventions operating in the study area. On Aug 23, 2021, questions were added to the study visit questionnaire to ask participants if they were receiving SMS health messages from programs other than the Mobile WACh NEO study. Because the study was intended to evaluate the impact of the SMS program without contamination, the primary intention to treat analysis will be adjusted by whether participants ever reported receiving maternal health related SMS messages from other programs. Secondary sensitivity analysis will use per-protocol analysis, excluding participants who reported receiving SMS messages from other programs and excluding intervention participants who never successfully received any SMS from the study.

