# Compared by linear GEE

#### **5.4 MISSING DATA**

Based on the Mobile WACh NEO pilot, we expect 10% loss to follow-up between enrollment and the 6-week study visit. We anticipate that dyads who are lost to follow-up are more likely to be disengaged from care and have experienced adverse outcomes. We also anticipate missingness may differ by arm, with the intervention arm having higher retention. Sensitivity analyses will be conducted for the primary mortality outcome assuming all missing participants did or did not experience neonatal mortality. If missing data rates were unexpectedly appreciably higher than these rates, more nuanced sensitivity analyses would be considered, such as those that consider differing rates of neonatal mortality for the missing participants that differ by arm. Variables with >10% missingness will be multiply imputed by MICE.

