Appropriate care-seeking outcome definition & analysis	20 April 2023	3.3	
 
Proportion of illness episodes with danger signs in which infant attended the clinic and/or infant was hospitalized independent of neonatal danger signs in the first 6 weeks of life Analyzed by log-binomial GEE
 
	
 
Proportion of illness episodes with danger signs in which infant attended the clinic and/or infant was hospitalized independent of neonatal danger signs during the study period (up to 18 weeks). If data is unavailable at the 6-week visit, data from the 2-week visit will be used. Analyzed by log-binomial regression
 
	Data collection error resulted in care-seeking only being collected for the most recent illness episode. 6-week visits could occur up to 18 weeks postpartum and we elected to include all data reported at study visits, regardless of when the care-seeking event occurred.
Approach to missing data	14 August 2023	3.4	Sensitivity analyses	Variables with >10% missingness will be imputed by multiple imputation by chained equations (MICE).	Two outcomes and one adjustment variable were found to have high levels of missingness. Multiple imputation has been shown to lead to less biased results than complete case analysis, and allows preservation of sample size.

Approach to exclusive breastfeeding cessation analysis	11 December 2023	3.5	Cox regression	For data imputed by MICE, use Poisson regression with time offset	Implementation of Cox regression with imputed data was unclear and Poisson regression is asymptotically equivalent.
Use of log-binomial vs Poisson regression	11 December 2023	3.5	Log-binomial regression	If any log-binomial regressions fail to converge, we will instead use Poisson regression with robust standard error	Log-binomial regressions frequently fail to converge. Poisson regression with robust standard errors yields asymptotic results.

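### The primary mortality model adjusts for a self-report collected after randomisation, and no comparison of the arms without that variable is designated

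*SAP*

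**What the plan says.** SAP section 4 commits the primary outcome to intention to treat with all participants, then adds that "the primary intention to treat analysis will be adjusted by whether participants ever reported receiving maternal health related SMS messages from other programs". The reason given is contamination: "After enrollment had begun, the study team became aware of other SMS health messaging interventions operating in the study area". On timing it says: "On Aug 23, 2021, questions were added to the study visit questionnaire to ask participants if they were receiving SMS health messages". The contamination sensitivity analysis uses the same report: "Secondary sensitivity analysis will use per-protocol analysis, excluding participants who reported receiving SMS messages from other programs". It also drops intervention women who never received a study SMS.

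Table 6.1 dates the change 27 March 2023 (version 3.2) and places it in the primary analysis. Section 6 discloses that changes after December 2022 came after the final DSMB meeting and did not have its approval.

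Section 5.3 item 1, Table 5.2 and Table 5.3 give log-binomial regression for mortality and name no covariate. Table 5.1 lists receipt of other SMS among the baseline characteristics, and section 5.2 brings any variable with a significant baseline difference into the primary model.

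On who is expected to drop out, section 5.4 says: "We anticipate that dyads who are lost to follow-up are more likely to be disengaged from care and have experienced adverse outcomes". On how the two arms should compare in this respect, it adds: "We also anticipate missingness may differ by arm, with the intervention arm having higher retention". Its rule for filling in values is: "Variables with >10% missingness will be multiply imputed by MICE". The entry of 14 August 2023 in Table 6.1 records: "Two outcomes and one adjustment variable were found to have high levels of missingness". It does not name them.

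**The concern.** Randomisation protects the comparison of arms as allocated. It does not protect a comparison within strata formed by something women report afterwards, knowing their arm. If reporting differs by arm and is also related to death or its causes, the adjusted estimate is biased even when the intervention does nothing.

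Both conditions are plausible here. Protocol 11.6.i schedules visits at enrolment, 2 weeks and 6 weeks postpartum, and SAP section 1 puts 75% of neonatal deaths in the first week, so a bereaved mother may be asked after the death or not at all. Section 5.4 expects loss to follow-up to be related to adverse outcomes and missingness to differ by arm; attendance decides how often a woman can report.

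Section 4 also does not say whether women never asked count as missing, which could bring in the imputation rule, or as not reporting. Two analysts could fit different primary models. If the unnamed adjustment variable with high missingness is this one, the primary result would rest partly on imputed values of it.

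**Working it through.** **The plan's own figure.** SAP section 3a has 2,500 per arm, 10% attrition, 23 per 1000 in control, HR 0.53, two-sided alpha 0.05 and at least 80% power; Table 3.1 gives 12.2 per 1000 in the SMS arm.

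- Evaluable per arm: 2,500 × 0.9 = 2,250.
- Expected deaths: 2,250 × (0.023 + 0.0122) = 79.2.
- HR: ln(1 − 0.0122)/ln(1 − 0.023) = 0.528.
- Schoenfeld power: Φ(√79.2/2 × |ln 0.528| − 1.96) = 81.2%.

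The figure reproduces, from a calculation with no covariate.

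**Bias under a true null.** Assumptions: mortality 0.023 in both arms; P(report | infant alive) = p, set by arm; P(report | infant died) = m × p. The values of p and m are mine. The adjusted estimate is the Mantel-Haenszel RR over two strata (reported, not reported); log-link Poisson and log-binomial models with main effects agree within 0.002.

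Worked case, control/SMS p = 30%/20%, m = 0.5. Each arm has 2,250 × 0.023 = 51.75 deaths.

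| | Control deaths / n | SMS deaths / n |
|---|---|---|
| Reported | 7.76 / 667.2 | 5.18 / 444.8 |
| Not reported | 43.99 / 1,582.8 | 46.58 / 1,805.2 |

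RR = [5.18 × 667.2/1,112.1 + 46.58 × 1,582.8/3,387.9] ÷ [7.76 × 444.8/1,112.1 + 43.99 × 1,805.2/3,387.9] = 24.86/26.54 = 0.937, where the truth is 1.00. Excluding reporters, as the per-protocol analysis does, gives (46.58/1,805.2)/(43.99/1,582.8) = 0.928, so it shares the bias.

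SE of log RR = √(2 × 0.977/(2,250 × 0.023)) = 0.194, giving a null 95% interval of 0.68 to 1.46. This unadjusted SE is used as an approximation throughout. Type I error = Φ(−1.96 − ln RR/0.194) + 1 − Φ(1.96 − ln RR/0.194).

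| Control/SMS reporting, m | Adjusted RR (true 1.00) | Type I error |
|---|---|---|
| 30/30, 0.5 | 1.000 | 5.0% |
| 40/20, 1.0 | 1.000 | 5.0% |
| 10/5, 0.5 | 0.974 | 5.2% |
| 40/20, 0.9 | 0.971 | 5.3% |
| 25/20, 0.5 | 0.969 | 5.3% |
| 30/20, 0.75 | 0.968 | 5.3% |
| 30/20, 0.5 | 0.937 | 6.3% |
| 40/20, 0.5 | 0.867 | 11.4% |
| 20/30, 0.5 | 1.068 | 6.3% |
| 20/40, 0.5 | 1.153 | 11.4% |

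**Attendance alone.** True exposure is 30% in both arms and P(report) = 0.30 × attendance. With attendance of 88% in control survivors, 60% in control bereaved, 92% in SMS survivors and 70% in SMS bereaved, RR = 1.005. With 85%, 50%, 95% and 50%, RR = 1.018 and type I error is 5.1%.

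**Does adjustment remove contamination?** Assume accurate reports and RR 0.53 in women without other SMS. Under full substitution, other SMS gives control women the whole benefit and SMS women nothing extra. At 30% exposure in control, the unadjusted RR is 0.53/(0.70 + 0.30 × 0.53) = 0.617. Adjusted values come from the main-effect log-link model on expected counts.

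| Other SMS, control/SMS | Mechanism | Unadjusted | Adjusted |
|---|---|---|---|
| 30/30 | substitution | 0.617 | 0.617 |
| 30/10 | substitution | 0.617 | 0.567 |
| 10/30 | substitution | 0.556 | 0.580 |
| 30/10 | independent, ×0.8 | 0.553 | 0.530 |

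Adjustment can do nothing, correct in part, move away from 0.53, or correct fully. Which of these applies depends on exposure by arm and on how other SMS acts, and the SAP states neither.

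**The case against.** The strongest reply is that the only mechanism the SAP itself anticipates, unequal attendance, moves the null by under 2% and leaves type I error at 5.0% to 5.1%. Values such as 0.87 or 1.15 need reporting to differ twofold by arm and bereaved mothers to report half as often, and nothing in the documents supports either. That stands; the case for change does not rest on a demonstrated size.

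Second, sections 5.3 and Tables 5.2 and 5.3 name no covariate, so crude mortality by arm would be published. The all-died and all-survived analyses and the Bayesian analysis are likewise silent on it. This is true, but silence does not designate an unadjusted test, while section 4 and Table 6.1 say expressly that the primary model is adjusted.

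Third, the trial does not allocate other programmes, and some answers may be antenatal or reflect exposure from before randomisation. That may be so, but the variable pools every visit, and the SAP neither separates these answers nor says which visits carried the question.

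Fourth, an effect free of contamination is a legitimate target, and adjustment sometimes approaches it. That supports a sensitivity analysis. It does not support replacing the randomised comparison.

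Finally, one could only add an unadjusted sensitivity analysis. That would supply the missing comparison but leave the headline estimate conditional on a report made after randomisation. Lack of DSMB approval reflects timing and is not evidence of rejection.

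**Conclusion.** The concern holds. The model for the sole primary endpoint of an unblinded trial conditions on a report collected after randomisation. No analysis without it is designated, and the per-protocol analysis cannot serve as a check because it conditions on the same report.

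The bias cannot be sized from the documents. On assumed reporting rates it runs from nil, through about 3% under mild patterns, to 13% to 15% when reporting differs twofold by arm and bereaved mothers report half as often. Its direction depends on which arm reports more. That the unnamed variable with high missingness is this one is an inference. The conclusion rests on the design and the wording of section 4. Since the change was made late, though openly dated, a designated unadjusted comparison matters more, and this should be settled before the primary result is reported.

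**What to change.** - In SAP section 4, make the primary mortality analysis the comparison of arms as randomised, without the other-SMS variable.
- Keep the adjusted model and the per-protocol analysis as labelled sensitivity analyses.
- In section 5.2, state that this variable may not enter through the baseline-imbalance rule. In Table 5.1, mark it as measured after randomisation.
- State which visits carried the question, and whether women never asked count as missing or as not reporting.
- Do not present a restriction to women who were asked as unbiased, because being asked depends on attendance after randomisation. If a restriction is wanted, define it by enrolment date, for example on or after 23 August 2021, which is fixed at randomisation.
- Log the change in Table 6.1.

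The cost is small: no new data, one analysis moved from primary to sensitivity, and one more documented late change to the primary model. An optional enrolment-date restriction would use fewer women and so have less power.

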## **5. STATISTICAL ANALYSES**

[figure not shown]
### **5.1 Study accrual**

Per CONSORT guidelines, we will report the number of individuals who:

1. Underwent screening
2. Met inclusion criteria
3. Did not meet inclusion criteria (and reasons)
4. Enrolled in the study and were randomized
5. Treated as per study protocol

The number of individuals enrolled and randomized per study month will be presented in a figure by study arm. No formal statistical testing will be performed. See Figure 5.1.

**Figure 5.1 – Trial profile**

## 5.2 Baseline Characteristics

We will describe the distribution of baseline characteristics, using summary statistics appropriate for the measurement scale. We will present these summary statistics in tables both pooled and by study arm (see Table 5.2). To determine if the randomization resulted in balanced groups, baseline characteristics will be compared between randomization groups using Chi-square tests for categorical variables and the Kruskal-Wallis test for continuous variables. Any variables found to vary significantly at baseline will be included as adjustments in the primary analysis.

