11.2 Study Area Description

Study sites: The proposed study will be conducted at 11 sites in Kenya: Mathare North City Health Centre, Riruta Health Centre, Rachuonyo South County Hospital, Ahero sub-District Hospital, Bondo District Hospital, Kisumu County Hospital, Migosi Sub-County Hospital, Lumumba Sub-County Hospital, Homa Bay County Referral Hospital, Rangwe Sub County Hospital and Rachuonyo North Sub County Hospital. Neonatal mortality in the Nairobi slum areas, Kisumu and Homa Bay counties is particularly high (4) so communities in these areas stand to benefit the most from the Mobile WACh NEO intervention. These facilities represent a mix of rural and urban facilities, all with sufficient patient volume to assure feasibility of recruitment. From our ongoing studies at these sites we estimate ~260 women attend ANC per month at each site.

Letters of cooperation will be submitted in a subsequent modification to this application.

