11.6 Data Collection Procedures

11.6.i. RCT

Intervention package: We propose to utilize Mobile WACH, a human-computer hybrid system used in our previous studies, which enables seamless two-way SMS communication and patient tracking, to provide consistent support to women and their infants during the peripartum period and 6 weeks into the baby's life. Women will receive automated theoretically grounded SMS messages targeting the appropriate peripartum period (Figure 10) and will have the capability to respond and spontaneously message a nurse based at the clinic. During pregnancy, automated SMS will be delivered weekly.

Two weeks prior to the participant's estimated due date (EDD), daily messaging will begin, and will continue for two weeks after delivery is ascertained. If delivery is not confirmed by 43 weeks gestational age, the participant will be automatically moved to the postpartum messaging track. Thereafter, SMS will be delivered every other day for the remaining four weeks. Automated SMS will be delivered at times and in languages based on patient preferences. We have partnered with a local premium rate service provider (PRSP), Africa's Talking, to provide SMS dialogue free of charge to participants. Women who experience pregnancy or infant loss will be enrolled into an infant loss track where they will receive messages of support.

[figure not shown]
[figure not shown]

Figure 10. Mobile WACH NEO intervention. Women who experience pregnancy or infant loss will be enrolled into an infant loss track where they will receive messages of support.

Randomization:

Participants will be randomized to 1) Interactive two-way SMS dialogue or 2) Control (no SMS), using 1:1 allocation. A randomization list will be generated by the study statistician using random block sizes in statistical software. Randomization will be stratified by site. This randomization list will be programmed into a computer program on an internet-based randomization platform. Each study site will be assigned unique user names and log in credentials for traceability purposes and ensuring that the randomization process is controlled. Study staff will use their unique credentials to log in to the randomization program. The program will display

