the allocation after staff have entered the participant ID. The allocation will be recorded in the program for further traceability. The study arm will be unblinded to participants and study staff. The control arm will receive standard care and education provided in ANC by MCH clinic staff. Because the study aims to determine mHealth benefits in addition to routine clinical care, MNCH services will be delivered by the MOH programs with minimal clinic interactions with study personnel. The intervention will be delivered between 28 weeks of gestation and 6 weeks postpartum.

Data collection:

Participants will be followed from enrolment (28-36 weeks gestation) up to 18 weeks postpartum. All clinical care will be managed through the existing MCH infrastructure. The study visit schedule will be aligned to routine postpartum and infant visits: enrolment visit in pregnancy (28-36 weeks gestation), 2 weeks postpartum and 6 weeks postpartum. Active tracing will be performed through phone calls and home visits to maximize completeness of data at study visits. Participants who do not report their delivery by 40 weeks will be contacted by phone, followed by home tracing if not reached by phone. Further, participants who are 1 week late for their 2-week or 6-week postpartum visits will be traced by phone. Participants who are 1 week late for their 6-week visit and cannot be reached by phone will be traced at their home. Participants who do not wish to come to clinic for their 2-week or 6-week visit will be offered to complete their visits **by phone or at home** in locations that ensure participant safety.

and confidentiality. This approach has been successful and acceptable in our previous studies in this population (31, 64, 69). During the consent process, study staff will collect contact information and permission to contact a family member or trusted individual who they may contact in case of long-term lack of communication from the participant. This person may be contacted as part of active tracing. In the case of a maternal death or disappearance, staff will collect information on the event from the provided contact.

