A tablet-based screening questionnaire will be used to assess eligibility and collect sociodemographic characteristics. Following enrolment in the RCT and randomization, a tablet-based enrolment questionnaire using an open-source tablet-based data collection system (Open Data Kit) will be used to collect enrolment data including: demographics, clinical and sexual history, family planning, experience with SMS and technology, social support, intimate partner violence, and depression.

At each visit, a standardized questionnaire will evaluate self-reported outcomes (Table 4), experience with the intervention (for intervention participants) and participant clinical characteristics that may be associated with the outcomes, such as delivery experience, maternal and child health status, breastfeeding, care-seeking, cord care, depression and social support. Between study visits, data will be abstracted from patient clinic records to ascertain clinical outcomes such as deliveries, clinic/hospital visits, and infant or maternal deaths (Table 4). The data will be abstracted from available facility records including MCH cards, facility registers (hospitalization, ANC, CWC, PNC), and EMR systems. The study nurses will review clinic records daily to check for deliveries and clinic visits from study participants. We have successfully employed this approach in a previous RCT, Mobile WACH-X (64). In addition to contributing to ascertainment of trial outcomes, abstraction of clinic records will enable personalization of messaging, for example initiating postpartum messaging after a participant delivers.

Medical extraction forms will be completed by data teams: delivery information, infant admissions, maternal health, infant health, maternal mortality, and infant mortality.

When the study team learns of an infant death through an SMS message, phone call or clinic record review, the study team will contact the participant to arrange a visit to conduct a verbal autopsy. Verbal autopsies will be performed about 6 weeks after the infant death, either in the clinic or at the participant's home based on their preference.

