**Sites:** Bondo District Hospital (Siaya County), Rachuonyo District Hospital (Homa Bay County), Mathare North City Council Clinic (Nairobi County), Riruta Health Centre (Nairobi County).

**Sample Size:** 5,000 pregnant women will be randomized (2,500 per arm)

**Duration:** Follow-up through 6 weeks postpartum.

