### 5.3 Analysis of study endpoints

1. **Neonatal mortality.** Among live-born infants, the proportion who die in the first 28 days postpartum will be compared between arms by log-binomial regression. As a *secondary analysis* of this outcome, a Bayesian analysis will be conducted using Markov Chain Monte Carlo modeling to estimate the probability that the Mobile WACh NEO treatment effect exceeds a range of potential values. Models with a range of prior probabilities will be developed.
2. **Early neonatal mortality.** Among live-born infants, the proportion who die in the first 7 days postpartum will be compared between arms by log-binomial regression.
3. **Initiation of early breastfeeding.** Proportion of infants who initiate breastfeeding in the first hour of life will be compared between arms by log-binomial regression.
4. **Cessation of exclusive breastfeeding.** Time to first introduction of complementary foods will be compared between arms by Cox proportional hazards regression.
5. **Bath.** Proportion of infants who are bathed in the first 24 hours of life will be compared between arms by log-binomial regression.
6. **Application of substances to cord.** Proportion of infants who have any substance applied to their cord will be compared between arms by log-binomial regression.
7. **Maternal provision of Kangaroo Mother Care (KMC).** Among women whose babies were born at <37 weeks gestation or weighing <2500g, proportion of who provide KMC on  $\geq 10$  of the first 14 days that the baby is home will be compared by log-binomial regression.
8. **Maternal knowledge of neonatal danger signs.** The mean number of 8 neonatal danger signs correctly named by mothers at the 2-week and 6-week visits will be compared between arms by Poisson generalized estimating equations (GEE). Exploratory analyses will evaluate time-dependent effects by incorporating timepoint as an interaction term.
9. **Appropriate care seeking.** The proportion of illness episodes with danger signs where the infant attended the clinic and/or where the infant was hospitalized independent of neonatal danger signs in the first 18 weeks of life (study follow-up period). Illness episodes are based on maternal self-report and only include the most recent illness episode at the 6-week visit, or 2-week visit if data is unavailable at the 6-week visit. Differences in proportions will be compared between arms by log-binomial regression.

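### Covariates for the primary analysis are chosen by baseline significance tests with no stated level, while site, the only stratification factor, appears in no endpoint model

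*SAP*

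**What the plan says.** SAP 5.2 tests baseline characteristics between arms with chi-square and Kruskal-Wallis tests, then applies this rule: "Any variables found to vary significantly at baseline will be included as adjustments in the primary analysis". No significance level is attached. The levels given elsewhere serve other purposes: 0.05 and 0.0045 are for endpoint power, and the 5% false discovery rate is for secondary endpoints (SAP Section 3).

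For the primary endpoint, SAP 5.3 item 1 says that "the proportion who die in the first 28 days postpartum will be compared between arms by log-binomial regression". A note to Table 5.2 gives robust Poisson regression as the fallback. SAP Section 4 fixes one covariate: "the primary intention to treat analysis will be adjusted by whether participants ever reported receiving maternal health related SMS messages from other programs".

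Protocol 11.6.i says "Randomization will be stratified by site" and names no other factor. No site term appears in SAP 5.3, in Table 5.2 or its notes, in the Table 5.3 footnotes, or in protocol Table 4. Clinic appears only as a row of the baseline shell, Table 5.1.

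Protocol 11.6.i places collection of depression and social support in the enrolment questionnaire, given after allocation: "Following enrolment in the RCT and randomization, a tablet-based enrolment questionnaire". It also says "The study arm will be unblinded to participants and study staff".

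On the number of sites, protocol 11.2 says "The proposed study will be conducted at 11 sites in Kenya", SAP Section 1 lists four facilities, and the Table 5.1 shell has six facility rows.

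**The concern.** There are four problems.

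- **The model is not fixed.** Which covariates enter depends on the observed imbalance and on a level nobody has stated. Under valid randomisation, a significant difference in a variable measured before allocation is a chance finding and says nothing about whether the variable predicts neonatal death.
- **The candidate list has moved.** SAP Table 6.1 records a new education cut-off (31 January 2023), removal of intended pregnancy (6 February 2023) and addition of other-program SMS (27 March 2023). SAP Section 6 says that changes after December 2022 were not approved by the DSMB. Nothing suggests that outcomes by arm drove these edits. Under the 5.2 rule, however, redefining a baseline row can change the primary model.
- **Some rows are not strictly baseline.** Depression and social support are recorded after an open allocation, so a difference could be a reaction to it. Adjusting would then remove something that allocation caused.
- **Site is left out.** When randomisation is stratified by a factor that predicts outcome and the analysis ignores it, standard errors come out too large.

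At stake are the credibility of the adjusted primary estimate and some precision on the common secondary endpoints.

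**Working it through.** **1. The plan's own power figure.** SAP Section 3a gives 2,500 per arm, 10% attrition, 23 per 1000 in control, HR 0.53 and two-sided 0.05; Table 3.1 gives 12.2 per 1000 in the intervention arm.
- Expected deaths: 2,500 x 0.9 x (0.023 + 0.0122) = 79.2.
- Schoenfeld power: Phi(sqrt(79.2/4) x |ln 0.53| - 1.96) = 80.6%, against the stated 80% or more.

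The figure reproduces, and this point does not alter it.

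**2. Chance that the rule adds a covariate.** Table 5.1 has 14 rows besides clinic: 9 sociodemographic, 2 obstetric and 3 mental health. Other-program SMS is already fixed, which leaves 13. With independent tests at level a, P(at least one enters) = 1 - (1 - a)^13, and the expected number is 13a.

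| Level (assumed) | At least one enters | Expected number |
|---|---|---|
| 0.01 | 1 - 0.99^13 = 12% | 0.13 |
| 0.05 | 1 - 0.95^13 = 49% | 0.65 |
| 0.10 | 1 - 0.90^13 = 75% | 1.3 |

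With an exchangeable correlation of 0.1, 0.3 or 0.5 between tests (300,000 draws), the 0.05 figure becomes 48%, 42% or 33%.

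**3. Could site enter through the Clinic row?** Site-stratified permuted blocks were simulated with 4, 6 or 11 sites, 300 trials each. The protocol gives no block sizes, so 4/6/8 was assumed and, in a separate run, 2/4/6. The chi-square test for clinic never reached p < 0.05, and the smallest p was above 0.99.

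**4. Cost of omitting site.** The standard error is inflated by about 1/sqrt(1 - SD^2/(p(1 - p))), where SD is the between-site standard deviation of the outcome proportion. The documents give no site-level rates, so each SD is an assumption.

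| Prevalence p | Assumed SD | SE inflation |
|---|---|---|
| 0.50 | 0.10 | 1/sqrt(1 - 0.01/0.25) = 1.021 |
| 0.50 | 0.15 | 1/sqrt(1 - 0.0225/0.25) = 1.048 |
| 0.40 | 0.10 | 1.022 |
| 0.40 | 0.15 | 1.050 |
| 0.023 (mortality) | 0.008 | 1.001 |

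**5. Mortality by simulation.** The setting was 11 sites, 4,500 births, 23 per 1000 in control, site SD 8 per 1000 and robust Poisson, with 1,000 trials per scenario.

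| | Without site | With site |
|---|---|---|
| Type I error (Monte Carlo SE 0.0075) | 0.060 | 0.061 |
| Power at RR 0.53 | 0.771 | 0.772 |

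The median SE ratio was 1.002, and the verdict differed in 0.1% of trials. A separate comparison set a Cochran-Mantel-Haenszel test stratified by site against the unadjusted two-proportion test (4, 6 or 11 sites; site rates from all equal up to about 6-55 per 1000; 20,000 simulations each). Stratifying gained at most about 0.7 power points, and type I error stayed between 4.6% and 5.3% for both tests.

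**The case against.** The strongest reply is that no harm to the main result is shown. The 49% is the chance that a covariate enters, not that the conclusion changes.

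A simulation of the screening rule supports this. It used 4,500 births, 13 independent binary variables at 40% prevalence, four of them prognostic with an assumed RR of 1.5 or 2, a 0.05 screen, robust Poisson and 1,500 trials per scenario. Type I error was 5.27% unadjusted and 5.20-5.27% with the rule. Power was 78.5-80.8% and 78.3-80.7%. The verdict differed in 0.3-1.0% of trials. This stands, provided imbalance arises by chance only; it does not cover rows affected by knowledge of allocation.

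Other parts of the reply also carry weight:

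- SAP 5.3 lists regression families and omits even the other-program SMS term, so its silence on site means site is not specified, rather than deliberately excluded.
- A level of 0.05 is the natural reading, so 49% is a fairer headline than the 12-75% range.
- The 2-5% figure rests on an assumed site SD, and the error is in the conservative direction.
- Six facility rows in an empty shell are weak evidence of a third site count. Eleven against four is a real conflict.
- Table 6.1 records no change to the 5.2 rule, so replacing it now is itself a late change. That calls for a dated entry and the arm-only result alongside; it is not a reason to keep the rule.

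**Conclusion.** The concern holds. As written, the adjusted primary model is settled only after baseline data by arm are seen. Its covariates are selected on imbalance at an unstated level, and the candidates include measures taken after open allocation. The rule can admit chance differences but practically never site, the one factor the design calls for.

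This is mainly a failure of pre-specification. At an assumed 0.05 level, there is a 33-49% chance that at least one extra covariate enters, depending on correlation. The mortality conclusion is little affected: the standard error is overstated by about 0.1-0.2% from omitting site, under an assumed between-site SD of 8 per 1000. For secondary practices such as bathing and cord care, at the 40-50% prevalence used in Table 3.1, the overstatement is about 2-5% under an assumed site SD of 10-15 points. The plan should be changed because the remedy is cheap, not because the primary result is in danger.

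**What to change.** 1. In SAP 5.2, delete the selection sentence and the tests behind it. Describe baseline characteristics by arm without p-values.
2. Reconcile the number of randomisation sites across protocol 11.2, SAP Section 1 and Table 5.1.
3. In SAP 5.3 and Table 5.2, put arm plus randomisation site in every primary and secondary model. Fix any pooling of small sites on enrolment alone, without reference to events or arm. One example is to pool a site with fewer than 200 women with the other sites of its county; that threshold is illustrative and not from the documents.
4. Allow further covariates only from a short named list measured before randomisation and chosen for prognostic value. Gestational age and maternal age qualify, since both are eligibility items.
5. State in 5.3 whether the other-program SMS term stays in the primary model or moves to a sensitivity model. A measure of ever having reported such messages is not fixed before randomisation.
6. Log the change with its date in Table 6.1 and report the arm-only estimate beside the adjusted one. The 14 August 2023 entry shows that data had already been examined for missingness.

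The cost is SAP wording, one log entry and an agreed site list. The drawback is that up to 10 site terms with about 79 expected deaths may stop the log-binomial model converging. That would trigger the planned robust Poisson fallback, which then applies to all comparisons of proportions.
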